- 128 predictability of the participants' clinical outcomes. In this application, we will evaluate the safety
- and feasibility of our CALEC product as well as its efficacy in treating the LSCD.
- 130

131 **2. STUDY AIMS**

132 The main aim of the study is to determine preliminary estimates of the safety and feasibility of

133 cultivated autologous limbal epithelial cell (CALEC) transplantation in the treatment of unilateral

LSCD. Secondarily, efficacy of CALEC will be investigated. This secondary objective is intendedto be exploratory rather than conclusive.

136

140

143

145

137 2.1. PRIMARY OBJECTIVES

- 138 1. **Safety:** To establish the safety of CALEC transplantation by determining the incidence of 139 primary ocular adverse events through 18 months of follow-up.
- 1411422. Feasibility: To establish feasibility of manufacturing CALEC for corneal surface reconstruction.

144 **2.2. SECONDARY OBJECTIVES**

- Efficacy: To investigate whether CALEC transplantation is efficacious in treatment of LSCD participants by comparing pre-operative to post-operative clinical parameters at months 3, 12, and 18.
- 149 150

151 2.3. STUDY CONCLUSIONS

152 The results of this Phase I/II study will provide guidance on whether to continue to a larger

153 Phase III study and will also provide preliminary data to help determine sample size for future

154 trials. Generally, if the study is not halted for feasibility issues, and there are no major safety or

155 efficacy concerns, a larger study of CALEC could be considered. However, caveats of the study

156 data and other potential factors outside of the trial will need to be considered and weighed in the

157 ultimate decision of whether to proceed.

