- **Transplant** anticipated to occur 10 to 30 days after biopsy
- Day 1, Week 1, Week 2*, and Month 1 Visits
 - Same for Phase A and B participants
 - Only required for participants who complete a transplant
 - Visit schedule is timed from transplant date
- 832 Month 3, 6, 9*, 12, 15*, and 18 Visits
- 833 834

829

830

831

- Same for Phase A and B participants
 - Only required for participants who complete a transplant
 - Visit schedule is timed from transplant date

836

835

* The 2 week, 9 month, and 15 month visits will be optional for participants for whom travel is
prohibitive. For participants who opt out of these visits, the clinical site will work with the
participant's usual care ophthalmologist on the following:

- 840 (1) Advise that the participant follows the protocol's post-operative medication regimen, 841 although the regimen will not be enforced by the protocol in these participants.
 - (2) Request adverse events be reported to the clinical site, under a medical release from the participant.
- 844

842

843

845

846 6.8.1. STUDY SCREENING

847 Prospective participants, as defined by the inclusion/exclusion criteria, will be considered for 848 entry into this study. The study design and treatment regimen will be discussed with each 849 participant. Written informed consent will be obtained before any study-specific screening 850 evaluations are performed. The following evaluations and procedures will be performed for all 851 participants during the screening period:

852 853

857

858

861

- Informed consent process culminating in signed consent document
- Eligibility Assessment
- Record current ocular and systemic medications
- Record medical/surgical history in the past 5 years
 - Record demographic data, including date of birth, sex, and race/ethnicity
 - Review of systems
- Blood draw for testing for confirmation of eligibility criteria, including:
- 860 o Hepatitis B
 - Hepatitis C
- 862 o HIV, AIDS
 - CBC (including platelet and hemoglobin levels)

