1127 7.3. OTHER OUTCOME MEASURES

1128 In addition to the primary and secondary outcome measures defined above, distribution of data 1129 and summary statistics will be evaluated on the following at each time point where relevant data 1130 are collected: IOP, impression cytology, corneal opacification, visual acuity, AS-OCT outcomes 1131 (central corneal epithelial thickness and limbal epithelial thickness in superior, inferior, nasal, 1132 and temporal quadrants), and IVCM outcomes (presence of corneal epithelial cells, presence of 1133 conjunctival epithelial cells, and the presence of limbal palisades of Vogt.) All reported adverse 1134 events will also be tabulated.

1135

1104

1105

1106 1107

1108

1109

1110

1111

1112 1113

1114

1115

1116

1117

1118

1119

1136 8. MONITORING STUDY PROGRESS

- 1137 Study progress will be monitored weekly or bi-weekly on Operations Committee calls.
- 1138 Recruitment reports will be available on the study website to monitor recruitment progress and
- 1139 ultimately follow up completion relative to the projected timeline. Operations Committee calls will
- also serve to keep all units of the Coordinating Center, Clinical Center, and PIs informed and
- 1141 engaged with the day-to-day progress of whether study goals are being met, including
- successful study oversight (including safety monitoring and protocol adherence monitoring of
- the monitoring plan) and eventually plans for closeout, manuscripts, and dissemination of study
- results. The Operations Committee will also monitor study progress with regards to timeliness
- 1145 and achievement of study goals.
- 1146

1148

1157

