1.0 Study Objectives

The objectives of the "Safety and Feasibility of Cultivated Autologous Limbal Epithelial Cell (CALEC) Transplantation in the Treatment of Limbal Stem Cell Deficiency" study are as follows.

Excerpt from Protocol Section 2:

The main aim of the study is to preliminary estimates of the safety and feasibility of cultivated autologous limbal epithelial cell (CALEC) transplantation in the treatment of unilateral LSCD. Secondarily, efficacy of CALEC will be investigated and both safety and efficacy of CALEC will be compared to CLAU. These secondary objectives are intended to be exploratory rather than conclusive.

PRIMARY OBJECTIVES

- 1. Safety (within CALEC group): To establish the safety of CALEC transplantation by determining the incidence of primary ocular adverse events through 18 months of follow-up.
- 2. Feasibility (within CALEC group): To establish feasibility of manufacturing CALEC for corneal surface reconstruction.

SECONDARY OBJECTIVES

- 1. Safety (CALEC versus CLAU): To investigate whether CALEC is similar to standard treatment with CLAU by comparing incidence of primary ocular adverse events through 18 months of follow-up
- 2. Efficacy (within CALEC group): To investigate whether CALEC transplantation is efficacious in treatment of LSCD participants by comparing pre-operative to post-operative clinical parameters at months 3, 12, and 18.
- 3. Efficacy (CALEC versus CLAU): To investigate whether CALEC is similar to standard treatment with CLAU by comparing between-group changes from pre-operative to post-operative clinical parameters at months 3, 12, and 18.

STUDY CONCLUSIONS

The results of this Phase I/II study will provide guidance on whether to continue to a larger Phase III study and will also provide preliminary data to help determine sample size for future trials. Generally, if the study is not halted for feasibility issues, and there are no major safety or efficacy trends that favor CLAU, a larger study of CALEC could be considered. However, caveats of the study data and other potential factors outside of the trial will need to be considered and weighed in the ultimate decision of whether to proceed.

13 14

15

16

17

18

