Efficacy Measures: Efficacy will be assessed in both CALEC and CLAU groups. The primary efficacy outcome will be a binary "Complete Success" of the graft, as defined below. Secondarily, "Partial Success" will also be considered according to a 3 category outcome defined below.

- 1. "Complete Success" will be defined as improvement in corneal surface integrity
- 2. "Partial Success" will be defined as
 - a. No improvement in corneal surface integrity and
 - b. Improvement in either
 - i. Extent of corneal vascularization or
 - ii. Participant symptomatology
- 3. Otherwise, not a success

Improvement in each area is defined as follows, where changes are measured relative to the Baseline visit:

- Corneal surface integrity
 - o Decrease in epithelial defect surface area (based on clinical assessment by an independent investigator, not the treating surgeon, as described in the MOP) by ≥75% or
 - o Decrease in corneal surface staining (based on clinical assessment by an independent investigator, not the treating surgeon, using NEI grading scale) by ≥50%
- Extent of corneal vascularization
 - Decrease in neovascular area (based on digital slit lamp photographs, using mathematical software to calculate as described in the MOP) by ≥25%
- Participant symptomatology

- o Decrease in Ocular Surface Disease Index (OSDI) score by ≥25% or
- o Decrease in Symptom Assessment in Dry Eye (SANDE) score by ≥25%

The primary efficacy time points will be at 3 months (to assess early success), as well as 12 and 18 months (to assess late success). Efficacy outcomes at all interim post-3 month time points will also be evaluated secondarily.

OTHER OUTCOME MEASURES

In addition to the primary and secondary outcome measures defined above, distribution of data and summary statistics will be evaluated on the following in both groups at each time point where relevant data are collected: IOP, impression cytology, corneal opacification, visual acuity. All reported adverse events will also be tabulated in both groups.

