 - iv. Comparisons between CALEC and CLAU will be made between the two Phase B (randomized) groups only by computing the differences in percentages and 95% confidence intervals around those differences, at each time point.
- 5. Secondary Efficacy Analyses (explore the individual efficacy outcome measures that contributed to the primary and secondary composite outcome measures): Efficacy will be explored by evaluating each outcome listed below at each protocol-specific time point
 - 1) Percentage change from baseline in frank epithelial defect surface area (clinical assessment*) -
 - 2) Proportion of participants with decrease in frank epithelial defect surface area (clinical
 - 3) Percentage change from baseline in surface staining (clinical assessment, NEI grading scale) -
 - 4) Proportion of participants with decrease in surface staining (clinical assessment ,NEI grading
 - 5) Percentage change from baseline in neovascular area (photographic images) continuous
 - 6) Proportion of participants with decrease in neovascular area (photographic images) by ≥25%

Continuous efficacy variables will be summarized by sample size, mean, median, standard deviation, minimum and maximum. Discrete efficacy variables will be summarized by frequencies and

These summary statistics will be presented within each of the following:

293

94 6 **Witi** 95 Only

Within-CALEC group: Evaluate in CALEC Group Phase A and Phase B participants combined. Only participants who completed transplant will be included.

o *CALEC versus CLAU comparison*: Evaluate within each treatment group, in Phase B participants only. All randomized participants will be included regardless of whether the transplant was completed. Phase B participants who discontinued prior to randomization will not be included.

• Exact 95% confidence intervals for the difference between treatment groups in means for continuous variables and in proportions will be provided.

Missing data will not be imputed for this secondary analysis.

Additional Tabulations and Analyses

Baseline demographic and clinical characteristics will be tabulated according to treatment group. Continuous variables will be summarized by sample size, mean, median, standard deviation, minimum and maximum. Discrete variables will be summarized by frequencies and percentages

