A flow chart will be constructed that accounts for all participants. Visit completion rates will be tabulated according to group. The percentage of participants with completed visits in window, out of window, and missed will also be tabulated. The number of dropouts and deaths and the completion rate excluding deaths will also be tabulated separately by treatment group.

Additional data related to both safety and efficacy will be explored by evaluating each of the following at each follow-up visit where data were collected as part of the protocol specified visit:

- Visual acuity
- IOP
- Corneal opacification
- Impression cytology results

Longitudinal models of these continuous measurements will be performed using mixed effects linear regression methods, including time by treatment group interactions.

Continuous variables will be summarized by sample size, mean, median, standard deviation, minimum and maximum. Discrete variables will be summarized by frequencies and percentages.

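### For the exploratory outcomes visual acuity, corneal opacification and (where numeric) IOP, the SAP specifies no within-participant change from Baseline and keeps a model contrast that no longer has a comparator

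*SAP*

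**What the plan says.** The secondary efficacy objective in Protocol 2.2 is to judge efficacy by "comparing pre-operative to post-operative clinical parameters at months 3, 12, and 18". SAP 1.0 repeats it. Neither place lists the parameters.

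Visual acuity, IOP and opacification are classed as other outcome measures. SAP 2.0 asks for summary statistics on them "at each time point where relevant data are collected: IOP, impression cytology, corneal opacification, visual acuity", and Protocol 7.3 has the same scope. Protocol 6.8.2 collects all three in both eyes at the Baseline visit.

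SAP 5.0, under Additional Tabulations and Analyses, is narrower: "Additional data related to both safety and efficacy will be explored by evaluating each of the following at each follow-up visit". It then states: "Longitudinal models of these continuous measurements will be performed using mixed effects linear regression methods, including time by treatment group interactions". Elsewhere in SAP 5.0, Secondary Efficacy Analyses item 5 specifies percentage change from baseline for epithelial defect area, staining, neovascular area, OSDI and SANDE. The SAP also says "Baseline demographic and clinical characteristics will be tabulated according to treatment group", without listing the variables.

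Protocol section 12 records that the CLAU comparison was discontinued after one participant had been randomised to CLAU.

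**The concern.** Acuity and opacity are outcomes a reader of an LSCD trial will look for, and the SAP itself describes these measures as bearing on both safety and efficacy. As written, the analysis yields a series of post-operative means and a model of post-operative values. Neither says how far an eye moved from where it started. Someone wanting that answer would have to set a follow-up mean beside a baseline mean as two group averages, which ignores that they come from the same eyes.

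The study is also meant to supply effect size and variability for later trials (SAP 4.0). For a pre- to post-operative design in vision, the useful quantity is the SD of change, and no planned table gives it. If the choice is left until the data are seen, how vision change is presented becomes a post hoc decision.

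**Working it through.** **Text comparison**

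| Question | Visual acuity, IOP, opacification | SAP 5.0 item 5 measures |
|---|---|---|
| Collected at Baseline? | Yes (Protocol 6.8.2) | Yes |
| Visits named in SAP 5.0 | Follow-up visits | Each protocol time point with data |
| Change from baseline specified? | No | Yes |
| Baseline in a model? | Not stated | No model specified |
| Contrast named | Time by treatment | Difference between groups |

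SAP 2.0 and Protocol 7.3 cover every time point with data, which includes Baseline. SAP 5.0 says follow-up visits. The two scopes differ, and neither mentions a paired change.

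**The plan's own figures.** The documents give no figure for acuity, IOP or opacification. The numerical support in SAP 4.0 concerns safety events with n = 15, and it reproduces:
- Chance of at least one event at a 5% rate: 1 - 0.95^15 = 0.537 (SAP 0.54).
- At a 20% rate: 1 - 0.80^15 = 0.965 (SAP 0.96).
- Exact 95% interval for 1/15: 0.2% to 32.0% (SAP 0 to 32%).

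None of these bears on this point.

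**Illustration of what pairing gains.** Inputs:
- n = 17, the transplant cap in Protocol 5.5. n = 15, the SAP 4.0 minimum with complete follow-up, is used as a check.
- Baseline to follow-up correlation r: not in the documents; assumed 0.5 to 0.8.
- Equal SD at both times: assumed. Results are in SD units, so no SD value is needed.

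Formulas for the 95% half-width:
- Unpaired: t(2n-2) × sqrt(2/n)
- Paired: t(n-1) × sqrt(2(1-r)/n)

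For n = 17, the unpaired half-width is 2.037 × sqrt(2/17) = 0.699. Paired:
- r = 0.5: 2.120 × sqrt(1.0/17) = 0.514, ratio 0.74, 26% narrower
- r = 0.7: 2.120 × sqrt(0.6/17) = 0.398, ratio 0.57, 43% narrower
- r = 0.8: 2.120 × sqrt(0.4/17) = 0.325, ratio 0.47, 53% narrower

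For n = 15, the unpaired half-width is 2.048 × sqrt(2/15) = 0.748. Paired it is 0.554 at r = 0.5 and 0.350 at r = 0.8, again 26% and 53% narrower.

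A lower correlation gains less. At r = 0.3 and n = 17 the paired half-width is 0.61, about 13% narrower.

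**Where numeric IOP change is possible.** Protocol 6.6.3 has recipient-eye IOP by palpation until the 13-week visit, and donor-eye IOP by palpation for one week after biopsy. A numeric change from an instrument reading is therefore not available at early recipient-eye visits. The wording leaves open whether the 13-week (Month 3) visit itself is by instrument.

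**The case against.** Four points count against a broader reading.

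1. A reader might infer that Baseline is left out altogether. The documents do not support that: SAP 2.0 and Protocol 7.3 ask for summaries at every time point with data, and baseline clinical characteristics are tabulated. This stands. What is missing is the paired change and the place of Baseline in the model.

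2. A reader might infer that the secondary objective goes unanswered. It does not. The efficacy outcomes designated for it, Complete and Partial Success, are defined relative to the Baseline visit (Protocol 7.2), and item 5 adds change from baseline for their components. The three measures here are exploratory additions.

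3. A reader might infer that attendance will distort the results. Protocol 6.8 says: "The 2 week, 9 month, and 15 month visits will be optional for participants for whom travel is" prohibitive. If, hypothetically, 4 of 17 skipped Month 9 and saw 0.5 logMAR worse than the other 13, the raw Month 9 mean would look 0.5 × 4/17 = 0.12 logMAR better with no eye changed. Nothing in the documents supports those inputs, Months 3, 12 and 18 are not optional, and a mixed model uses incomplete sequences. The argument touches only raw means at the optional visits.

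4. The SAP plans no interval from unpaired means, and a mixed model does separate between- from within-participant variance. Both are true, so the percentages above show the value of pairing and do not measure an error in a planned result. The model still has no stated Baseline reference.

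It may also be said that the model was written for two arms and would have to be rewritten for one anyway. That is a good moment to name the contrast that replaces time by treatment.

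**Conclusion.** The point holds in a limited form. For visual acuity and opacification, and for IOP where a numeric reading exists, the SAP's analysis text specifies raw follow-up values and a time by treatment model, and estimates no within-participant change from Baseline. With CLAU discontinued and one CLAU participant randomised, the model's named contrast has no usable comparator. The remaining time effect describes drift among post-operative visits unless Baseline is brought in.

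The consequence is modest. It concerns exploratory other outcomes, and no primary safety, feasibility or graft-success result changes. The gain of about 26% to 53% in interval width rests on the assumed correlation of 0.5 to 0.8 and equal SDs. It hardly depends on whether n is 15 or 17, and it shrinks at lower correlations. The case for acting is that the better analysis uses data already collected.

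**What to change.** Amend SAP 5.0, Additional Tabulations and Analyses, as follows:

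- Align its scope with SAP 2.0, so that Baseline is included among the summarised time points.
- Report recipient and donor eyes separately.
- Visual acuity: within-participant change from the Baseline visit at each visit, with SD and 95% CI. Acuity is recorded as Snellen (Protocol 6.6.2), so state the rule for conversion to logMAR, or cite the Manual of Procedures if it is there.
- Opacification: a baseline-by-visit shift table of Fantes grade, which is an ordered scale.
- IOP: numeric change only at visits where both readings are by instrument. State how palpation results are tabulated, and whether Month 3 counts as an instrument visit.
- Model: replace the time by treatment term with a within-CALEC contrast against Baseline. Either make Baseline the first level of a categorical time factor, or model change with centred Baseline as a covariate so that the intercept at each visit is the mean change.
- Name Months 3, 12 and 18 as the main time points and treat other visits as supportive.

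Impression cytology has no Baseline value and stays a follow-up summary. The cost is SAP wording and a few table columns, with no new data, visits or participants. It should be done before the data are analysed.

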- 634 participant will be asked to put a mark on two given lines to depict the extent of their symptoms
- 635 separately in terms of frequency and severity the mark will be measured and recorded by the 636 study team.
- 636 s 637

638 6.6.2. VISUAL ACUITY

- At each visit, participants' best corrected visual acuity (BCVA) of both eyes will be assessed by
 Snellen visual acuity and recorded (MOP, Section 23). Manifest refraction will be performed if
 pinhole improves BCVA more than 1 line.
- 642

643 6.6.3. INTRAOCULAR PRESSURE (IOP) EVALUATION

- IOP will be evaluated by one or a combination of the available modalities noted below
 depending on the cooperation of the participant and ocular appearance on the exam as well as
 ability to obtain the reading (MOP, Section 24).
- Tonopen: To measure IOP using tonopen applanation, the Tono-Pen XL (Mentor, Santa Barbara, CA) will be calibrated daily. Following administration of 0.5% proparacaine hydrochloride in the cul-de-sac, the pen tip (with disposable cover) will be touched to the central cornea until a reading is measure. Only measurements with a 5% standard error will be accepted. If error is greater than 5%, the measurement will be repeated.
- Pneumotonometry: Pneumotonometer (Reichart) measurements will be taken
 perpendicularly to the cornea, at the center of the cornea after calibration according to
 the manufacturer's instructions in the event Tonopen is unable to provide a reading
- Palpation: The IOP of the donor eye will be determined by palpation for one week post
 biopsy. The IOP of the recipient eye will be determined by palpation until the thirteen
 week visit after transplant.
- 658

659 **6.6.4. SLIT LAMP EXAMINATION**

- At each visit, participants will undergo assessment of eyelid, conjunctiva, cornea, and all
 intraocular structures of both eyes, by a certified study investigator who was not the investigator
 performing the biopsy or transplant for that participant. This may include a research associate or
- research fellow who does not perform surgeries but functions as a clinical examiner investigator
- only. The number of such investigators will be limited and each will complete sample
- assessments on the primary efficacy endpoints (both the corneal epithelial defect surface area
- and NEI scale gradings noted below) as part of their study training and certification.

667

671

668 6.6.4.1. CORNEAL OPACIFICATION

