669 The cornea will be examined and its opacification will be graded according to the Fantes Scale 670 (MOP, Section 26) (Fantes et al., 1990).

672 6.6.4.2. CORNEAL FLUORESCEIN STAINING

673 For the clinical exam with corneal fluorescein staining, a single Akorn FUL-GLO Fluorescein

674 Sodium strip will be wetted with a drop of sterile saline and applied to the inferior fornix and

675 examination and photography (Section 6.6.7.2 below) will be performed between 2-5 minutes 676 after the instillation of fluorescein.

677

678 The entire cornea will be examined using slit lamp evaluation with a yellow barrier filter (#12 679 Wratten) and cobalt blue illumination (staining is more intense when it is observed with a yellow 680 filter). Staining with fluorescein will be used to determine presence of corneal epithelial defects. 681 The extent of corneal fluorescein staining will be evaluated using the National Eve Institute (NEI) grading scale (MOP, Section 25). Each of five corneal zones (superior, nasal, central, 682 683 inferior, and temporal) will be graded from 0 (normal) to 3 (severe) and staining score of the 684 cornea will range from 0 and 15 points. Epithelial defects (as defined as confluent epithelial 685 staining of >1 mm^2) will be measured at the greatest horizontal and vertical dimensions, and 686 surface area will be calculated in mm².

687

688 **6.6.5. SCHIRMER'S TEST**

689 The Schirmer's test will be performed with anesthesia by placing a narrow filter-paper strip

690 (5mm × 35mm strip of Whatman #41 filter paper) in the inferior cul-de-sac (MOP, Section 27).

- This test is to be conducted in a dimly lit room. The participant will be instructed to gently close
- their eyes until five minutes have elapsed. The strips will be removed. Since the tear front will
- 693 continue advancing a few millimeters after it has been removed from the eyes, it is important to
- 694 mark the tear front with a ball-point pen at precisely five minutes. Aqueous tear production will
- be measured by the length in millimeters that the strip wets in 5 minutes.

696

697 6.6.6. IMPRESSION CYTOLOGY

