At 12, 15, and 18 months after transplantation, if there is clinical suspicion of limbal stem cell deficiency in the recipient eye, an impression cytology of the ocular surface will be performed to confirm the diagnosis. Impression cytology will be performed in the recipient eye after application of the topical anesthetic. Nitrocellulose membranes will be firmly pressed onto the ocular surface (as shown in MOP) for 5 seconds. Each membrane will cross the limbus so as to collect cells from the cornea, the limbus, and the conjunctiva. The membranes will then be removed and fixed in methanol solution immediately. Samples will then be taken to the

- 705 pathology laboratory for further staining and analysis.
- 706

707 6.6.7. SLIT LAMP PHOTOGRAPHY

708Digital corneal photography to measure neovascular area and epithelial defect area will be done709by a certified study photographer or research associate, using a slit lamp with a digital camera

- 710 attachment and a flash-through-the-slit illumination system.
- 711

712 6.6.7.1. PHOTOGRAPHY FOR NEOVASCULAR AREA

713 The entire cornea will be pictured using diffuse illumination and 10x magnification. If lids are

- drooping, the photographer will attempt to gently remove them from area of focus with a cotton
- swab. Participants with dark irises, which may prohibit a clear image, may be dilated with
- tropicamide only (without use of an adrenergic agent that may induce vascular 'blanching') to
- enhance visualization of corneal blood vessels. Digital photographs will be taken and the

images will be uploaded into the graphics editing software (ImageJ). The neovascular area will

- be calculated as described in MOP. Digital slit lamp corneal pictures will be analyzed using
- graphics-editing software (Photoshop) and a mathematical program (Matlab script). After the
- total area is delineated, the blood vessels will be isolated using Photoshop. Neovascular area
 (in pixels) is computed using a Matlab script to assist a qualified technician to measure the area
- 723 of the vessels themselves.
- 724

725 6.6.7.2. PHOTOGRAPHY FOR EPITHELIAL DEFECT AREA

- For photography with corneal fluorescein staining, a single Akorn FUL-GLO Fluorescein Sodium
- strip will be wetted with a drop of sterile saline and applied to the inferior fornix and examination
- (Section 6.6.4.2 above) and photography will be performed between 2-5 minutes after the instillation of fluorescein.
- 730

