14.4. APPENDIX IV: FANTES SCALE FOR CORNEAL OPACITY							
Grade	Description						
0	Totally clear such that no opacity could be seen by any method of slit lamp microscopic examination						
0.5	A trace or a faint corneal haze seen only by indirect broad tangential illumination						
1	Haze of minimal density seen with difficulty with direct and diffuse illumination						
2	A mild haze easily visible with direct focal slit illumination						
3	A moderately dense opacity that partially obscured the iris details						
4	A severely dense opacity that obscured completely the details of intraocular structures						

Safety and Feasibility of Cultivated Autologous Limbal Epithelial Cell Transplantation in the Treatment of Limbal Stem Cell Deficiency

1470 1471 14.5. APPENDIX V: IMPRESSION CYTOLOGY

Reporting:
-

Region	Goblet Cells Cornea
Superior	
Inferior	
Temporal	
Nasal	

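### The SAP assigns one linear mixed model with a treatment interaction to acuity, IOP, Fantes opacity grade and impression cytology, which does not fit how the protocol collects them or its single CLAU participant

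*SAP*

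**What the plan says.** SAP 5.0, under Additional Tabulations and Analyses, names four items to examine at each follow-up visit with data: visual acuity, IOP, corneal opacification and impression cytology. It continues: "Longitudinal models of these continuous measurements will be performed using mixed effects linear regression methods, including time by treatment group interactions". Two general rules follow. Continuous variables get means, medians, SDs and ranges, and "Discrete variables will be summarized by frequencies and percentages". The SAP does not say which of the four items fall under which rule. It gives no scale, eligible visits or random-effects structure for any of them.

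The protocol describes the data as follows.

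- **Opacification** (6.6.4.1, Appendix IV): "opacification will be graded according to the Fantes Scale". The scale has six descriptive grades: 0, 0.5, 1, 2, 3 and 4. Grade 0.5, for example, is "A trace or a faint corneal haze seen only by indirect broad tangential illumination".
- **Impression cytology** (6.6.6): at months 12, 15 and 18 only, and only "if there is clinical suspicion of limbal stem cell deficiency in the recipient eye", to confirm the diagnosis. It is not among the screening or baseline procedures (6.8.1, 6.8.2).
- **IOP** (6.6.3): Tonopen, with pneumotonometry if the Tonopen gives no reading. However, "The IOP of the recipient eye will be determined by palpation until the thirteen" week visit after transplant. The donor eye is palpated for one week after biopsy.
- **Visual acuity** (6.6.2): best-corrected Snellen. Neither document states a conversion to a numeric scale or a rule for off-chart vision.

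On groups, SAP 4.0 expects 13-15 CALEC and 6-8 CLAU participants in Phase B. Protocol section 12 records that the CLAU comparison was discontinued when one participant had been randomized to CLAU. Protocol 5.5 now ends enrollment at 17 CALEC transplants at the latest.

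**The concern.** The sentence treats four differently measured outcomes as one kind of data and attaches a group comparison that the trial no longer makes. Followed literally, it has three consequences.

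- It produces a treatment-by-time estimate resting on one CLAU participant.
- It fits a linear trajectory to a cytology subset selected because the outcome was suspected.
- It yields IOP models whose coverage of follow-up is not stated. The early recipient-eye visits, which fall within the protocol's topical steroid schedule (6.5.4), have no tonometer value. A model that starts at month 3 could be taken to cover all of follow-up.

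If the sentence is not followed literally, the analyst has to choose scales, visits and methods for each outcome after the data are in.

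**Working it through.** The plan gives no figure for these models, so there is nothing to reproduce. The check sets the model against each outcome as collected, then looks at the interaction.

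**1. Outcome against model**

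| Outcome | As collected | Fit to a linear mixed model |
|---|---|---|
| Opacification | Six ordered grades | Runs, but only as an approximation |
| Impression cytology | On suspicion, months 12/15/18, no baseline | Unsuitable |
| Visual acuity | Snellen | Suitable after a conversion that is not stated |
| IOP | Tonometer, with palpation early on | Suitable for tonometer readings only |

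**2. Fantes spacing.** The step from 0 to 0.5 is 0.5 and the step from 3 to 4 is 1. A linear model therefore counts the second change as 1 / 0.5 = 2 times the first. The verbal grade descriptions give no basis for that ratio.

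**3. Cytology records.** Each eye contributes between 0 and 3 records, none at baseline. An eye contributes only if LSCD was suspected, so the modelled eyes are not a sample of the transplanted eyes.

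**4. IOP visits.** The post-transplant schedule has ten visits: day 1, weeks 1 and 2, and months 1, 3, 6, 9, 12, 15 and 18. Recipient-eye palpation covers the first four, leaving 10 - 4 = 6. This reads Protocol 6.6.3 as returning to tonometry at the 13-week (month 3) visit itself. For the donor eye, palpation ends 7 days after biopsy and transplant is anticipated 10 to 30 days after biopsy (6.8). As scheduled, no post-transplant donor-eye visit is affected.

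**5. The interaction.** With equal between-person variance, the standard error of a between-group contrast is proportional to sqrt(1/n_CALEC + 1/n_CLAU).

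- Planned Phase B, 21 randomized 2:1, so 14 v 7: sqrt(0.0714 + 0.1429) = 0.463.
- Current protocol, 17 v 1: sqrt(0.0588 + 1) = 1.029.
- Ratio: 1.029 / 0.463 = 2.22.
- Share of the 17 v 1 variance due to the one CLAU participant: 1 / 1.0588 = 94%.

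A simulation agrees. It used 100 data sets per setting, visits at months 3 to 18, and assumed SDs of 1 for intercepts, 1 for slopes and 0.5 for residuals.

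| Median SE of interaction | 14 v 7 | 17 v 1 | Ratio |
|---|---|---|---|
| Continuous, random intercept | 0.38 | 0.87 | 2.29 |
| Continuous, random slope | 0.56 | 1.25 | 2.23 |
| Fantes-graded, random intercept | 0.39 | 0.88 | 2.26 |
| Fantes-graded, random slope | 0.52 | 1.19 | 2.29 |

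At 17 v 1 the model returned an estimate in 99 or 100 of 100 runs. Leaving out random slopes that were present raised false-positive rates to 15-19%, against 4-11% with them included. The Monte Carlo error on those rates is about 2-4 points. The SAP does not state which structure would be used.

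**The case against.** The best defence is that the sentence covers only the continuous members of the list. The discrete-variable rule follows directly, so Fantes grade and cytology might simply be tabulated. That reading is possible. But the word *these* follows all four items, and nothing says which are discrete, so the plan does not settle it.

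Several stronger readings are tempting, and the documents do not support them.

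- **All four outcomes are non-continuous.** Tonometer IOP is continuous, and its Tonopen acceptance rule is numeric ("Only measurements with a 5% standard error will" be accepted). Acuity can be modelled once converted.
- **The analysis is invalid or cannot be run.** The interaction model runs at 17 v 1, on graded data as well. Grading changed the standard error little (0.56 to 0.52 at 14 v 7 with random slopes).
- **Palpation visits leave no recorded value, or cytology is categorical.** How palpation is recorded is not shown. Appendix V gives a goblet-cell entry by region without its scale. The Manual of Procedures, which was not available, may settle both, and may also hold an acuity conversion.
- **The SAP would overstate recurrent LSCD by dividing by tested eyes.** It names no denominator for cytology, so no size can be put on such an error.

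It is also fair to say that the interaction is left over from the two-arm design and has nothing to do with outcome scale. It still sits in the same sentence and has to be removed there.

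**Conclusion.** The sentence is wrong as written, with limited consequences. It misdescribes Fantes grade as continuous, does not suit cytology collected only on suspicion, and leaves acuity without a stated scale. It is silent on the four recipient-eye visits assessed by palpation. The treatment interaction can be computed but cannot be read as a treatment effect: about 94% of its sampling variance would come from one CLAU participant, assuming 17 CALEC participants and equal between-person variance. The simulated standard errors depend on assumed SDs, but the ratio of about 2.2 to 2.3 follows mainly from the group sizes.

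These outcomes are exploratory. Protocol 7.3 asks only for distributions and summary statistics, and no primary or secondary safety, feasibility or efficacy result rests on these models.

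**What to change.** Replace the sentence with a short rule for each outcome.

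- **Groups:** drop the treatment interaction. Use time-only models in CALEC participants, and state the random effects.
- **Visual acuity:** linear mixed model on logMAR, with the conversion and an off-chart rule stated.
- **IOP:** linear mixed model on tonometer readings. For the recipient eye, use month 3 onward against baseline. For the donor eye, use all visits with a tonometer reading. State that palpation readings are excluded from the model.
- **Fantes grade:** shift table from baseline, or an ordinal model.
- **Impression cytology:** no model. Give tested and confirmed counts beside the number of transplanted eyes seen at that visit. A count of suspected eyes is not proposed, because the documents do not show that suspicion is recorded at each visit.

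The cost is one SAP paragraph and no new procedures. The small downside is fewer recipient-eye IOP visits in the model: six scheduled post-transplant visits instead of ten.
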